	Gadoteric Acid Meglumine Salt: Patients who have undergone contrast-enhanced MRI using Gadoteric Acid Meglumine Salt contrast agent for clinical purposes.	Drug: Gadoteric Acid Meglumine Salt Injection (Jia Di Xian™)
Eligibility Criteria	
Inclusion Criteria:
 
 1. Patients aged 18 to 80 years old who require gadolinium-based CE-MRI; 2. Patients with renal function $30\text{ml/min}/1.73\text{m}^2 \leq \text{eGFR} < 90\text{ml/min}/1.73\text{m}^2$; 3. Patients who are able and willing to comply with the required inspection requirements. 
Exclusion Criteria:
 
 1. Patient who experienced allergic reactions to previous gadolinium based contrast agents; 	

	
 2. Patient who had used gadolinium based contrast agents within 3 months; 3. Patient with acute renal failure; 4. Patient who cannot comply with or cannot tolerate the necessary fluid replenishment procedures; 5. Patient with major mental illness, impaired consciousness or other diseases considered by researchers to affect observation.
Outcome Measure	
Primary Outcome indicators: Record the incidence of various adverse events;
 
Secondary outcome indicators:
 
 1. Changes of serum creatinine and inflammatory factors (TNF-α, hs-CRP, IL-6) before and after CE-MRI 2. Patient skin examination and evaluation: evaluation of relevant indicators of skin biopsy (proliferation of fibroblasts in subcutaneous tissue, thickening of collagen fiber bundles)
Enrollment	600 participants

I. Sponsor Information

(I) Name of sponsor

[name]

(II) Address of sponsor

Lishui Central Hospital, [name]

(III) Contact information of sponsor

[name]

(IV) Relevant qualification documents of sponsor

The relevant qualification documents of the sponsor will be provided in a separate letter.

II. Purpose and contents of clinical trial

(I) Purpose

To compare the incidence of adverse events of linear and macrocyclic gadolinium-based contrast agents for patients with mild to moderate renal insufficiency undergoing enhanced magnetic resonance imaging.

(II) Contents

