Visit 4: within 6 months after contrast injection;

Visit 5: within 12 months after contrast injection;

Visit 6: within 24 months after contrast injection;

Visit content: study-CRF table-patient basic information table

Visit 1: study-CRF table-patient basic information table

1. Name of hospital:
2. Registration Date:
3. Contact details of the patient/its agent:
4. source: Outpatient () Hospitalized ();
5. Clinical department;
6. Name:
7. Sex: Male () Female ();
8. Age:
9. Weight: Kg;
10. Height: CM;
11. CE-MRI informed: yes () no ();
12. CE-MRI Indications:

13. Gadolinium contrast injection time:

14. Gadolinium contrast agent injection volume: ml;

15. Gadolinium contrast injection method: Push () Machine injection () (Please mark the injection speed);

16. Previous image enhancement examination history: time; Contrast agent name; Yes/No adverse events occurred;

a) yes time symptom severity;

17. Past history of adverse drug reactions: yes/no, yes time、AE symptom、severity;

18. The latest serological examination before CE-MRI and the serological examination within 2 weeks after CE-MRI;

19. History of allergy: yes/no, yes, allergy description;

20. Suspected existing disease:

21. Existing disease treatment plan: medical treatment () oral () Intramuscular injection () Intravenous injection () Surgical treatment () surgical intervention () Else;

22. History of illness:

a) Disease name Date of diagnosis duration;

23. Daily medication (Take medication within 1 week):

a) Generic name of the drug Taking method dose

24. Other information

25. Adverse event: yes () no ()

Visit 2, Visit 3, Visit 4, Visit 5 and Visit 6 Study-CRF Form-Contrast Adverse Events

1. Name:
2. Sex:
3. Age:
4. Weight:
5. Time to onset of adverse events:
6. Severity assessment:
7. Suspected drugs: Generic name (including dosage form)、Manufacturer、Production batch、Dosage、Start and end time of medication、Reason for medication;

8. Concomitant drugs: Generic name (including dosage form)、Manufacturer、Production batch、
Dosage、Start and end time of medication、Reason for medication

Concomitant drugs are those used within 24 hours;

9. Other suspected factors: Such as: patient disease progression, patient treatment plan, etc.;

10. Adverse events affect organ systems:

11. Adverse event name: refer to MedADR glossary;

12. Process description and handling of adverse events (attachment available);

13. Adverse event results:

Recover () Improve () Not getting better () Unclear ()

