Have adverse events () manifestation: _____

death () Direct cause of death: _____ Time of death: y m d

14. Impact on the original disease:

Not obvious () Prolonged course () Worsening () Cause adverse events () Cause death ()

15. Whether the withdrawal/reduction reaction is reduced or disappeared:

yes () no () unclear () No discontinuation or dose reduction ()

Whether the same reaction occurs again after re-use

yes () no () unclear () Unused ()

16. Relevance evaluation:

Certain () Very likely () Possible () May be irrelevant ()

Wait to be evaluated () Can't evaluate ()

17. Reporter's information: name, contact number, email address, occupation

(IV) Evaluation Standard

1. Adverse events

Adverse Event (AE) : Adverse clinical events that occur during the course of drug treatment may not necessarily have a causal relationship with the drug.

Serious Adverse Event (Serious Adverse Event, SAE): the reaction of one of the following

damages caused by the use of drugs:

- 1) Cause death;
- 2) Life threatening;
- 3) Carcinogenic, teratogenic, and birth defects;
- 4) Cause significant or permanent human disability or damage to organ function;
- 5) Lead to hospitalization or prolonged hospital stay;
- 6) Causes other important medical events, if not treated, the conditions listed above may occur.

Report serious adverse events:

- 1) When an aggregated, serious, or new (not listed in the ACR Contrast Media Guide) adverse reaction occurs, the investigator must within 24 hours of being notified:
- 2) Fill in the "Adverse Event/Reaction Report Form" and report to the Research Center Ethics Committee;
- 3) Entering adverse reaction events into EDC allows researchers to process relevant safety information/take corresponding measures immediately;
- 4) When a known mild to moderate adverse reaction occurs, the researcher needs to fill in the "Adverse Event/Reaction Report Form" within 15 days after being notified, and complete the entry of the adverse reaction event into the EDC to facilitate timely information about the adverse event;

2. Severity assessment

AE severity refers to the degree of occurrence of a specific event (which can be SAE or ordinary AE), but the event itself may have relatively small medical significance.

Principle of severity

Mild symptoms or signs that are easily tolerated

Moderate symptoms and signs cause discomfort and affect daily life;

Severe Cannot engage in daily life or work, need sick leave or necessary treatment.

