3. Causality assessment

The causal relationship between adverse events and drugs is often based on the investigator's clinical judgment and understanding of the trial drug, but generally can be comprehensively analyzed from the following aspects:

The time relationship between medication and adverse events and whether there is a

dose-effect relationship;

Whether it is a known type of drug reaction;

Whether the adverse events alleviate or disappear after stopping or reducing the dose;

Under strict and safe conditions, when the test is repeated, whether the adverse event recurs;

Whether adverse events can be explained by the effects of concomitant medications, the patient's disease progression, and the effects of other treatments;

The causal relationship between adverse events and drugs can be judged according to the WHO Uppsala ADR Testing Center Guidelines. The six-level evaluation standard is affirmative, very likely, possible, unlikely, unassessed, unable to assess.

VII. Trial quality control

The quality of clinical trials refers to its scientificity, reliability, accuracy and completeness.

Quality assurance is an important cornerstone of whether the trial can be successful. As a quality management standard, GCP is its tenet and goal to ensure quality. GCP's methods and measures to ensure the quality of clinical trials mainly include the following:

To specify the qualifications and responsibilities of all relevant personnel in clinical trials;

To stipulate the conditions, procedures and contents of the trial plan for conducting clinical trials;

Specify test records, reports, data processing and archiving systems;

To stipulate management systems for the preparation, distribution, use, and recovery of experimental drugs;

Develop and follow standard operating specifications (SOP) to regulate various tests and operations;

Establish a multi-step quality assurance system;

Contains 4 links: quality control, supervision, inspection and inspection.

(I) Quality Control

PI is fully responsible for quality control, and each researcher or other participating personnel

implements and executes it.

1. Qualifications and responsibilities of test personnel

The investigator is a key factor for the success of clinical trials. Whether it can be completed smoothly and with high quality depends mainly on the investigator. Combined with ICH-GCP, foreign scholars have summarized 12 gold standards for qualified researchers, as follows:

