Taking adverse reactions and adverse events as dependent variables, taking gender, age, concomitant diseases, gadolinium diamine, gadoteric acid meglumine exposure, combined medication and other factors as independent variables, using Logistic regression to analyze the occurrence of adverse reactions or adverse events. Significant influencing factors, and estimate the odds ratio and its 95% confidence interval. The variables entered into the model will be confirmed in the statistical plan before the data is locked.

X. Trial summary and results publication

After the drug clinical trial summary is completed, at least there should be a statistical analysis report and a clinical trial summary report; after consultation with the investigator, the trial protocol or the results of the analysis after the analysis can be published, and the disclosure of confidential data is strictly prohibited.

The statistical analysis report is completed within one month after the database is locked, and the clinical trial summary report is completed within one month after the statistical analysis report is completed.

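### Adverse reactions are classified with the agent apparently known and then regressed on the agent, unranked against all adverse events, so differential attribution could create a false agent difference

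*Combined protocol and SAP*

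**What the plan says.** **Causality.** Section VI (IV) 3 describes attribution as "often based on the investigator's clinical judgment and understanding of the trial drug". It goes on to list aspects to weigh: timing, dose-effect, response to stopping, recurrence on repeat and other explanations. One further aspect is "Whether it is a known type of drug reaction". The rating scale follows: "The six-level evaluation standard is affirmative, very likely, possible, unlikely, unassessed, unable to assess". No cut-off says which levels make an event an adverse reaction.

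**Event form.** In section VI (III), item 7 of the form used from Visit 2 onward starts "Suspected drugs: Generic name (including dosage form" and goes on to manufacturer, batch, dosage and medication times. The causality rating, "16. Relevance evaluation", is on the same form. No masked rating or independent adjudication is described.

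**Analysis.** Section IX (II) 3 reads: "Taking adverse reactions and adverse events as dependent variables, taking gender, age, concomitant diseases, gadolinium diamine, gadoteric acid meglumine exposure". It does not rank the two outcomes. The same section also reports adverse reactions and serious adverse reactions with their own incidences and intervals.

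**Outcome.** The Protocol Summary has "Primary Outcome indicators: Record the incidence of various adverse events". Section VI (IV) 1 defines an adverse event without requiring causality, but defines a serious adverse event as damage caused by the drug.

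**The concern.** An adverse reaction is an adverse event that has passed a causality judgement. If the rater knows the agent and may use what is known about it, the outcome is partly shaped by the exposure against which it is later tested. Two identical events can then be counted for one agent and dropped for the other. Adjusting for sex, age, concomitant disease or medication does not remove this, because the bias lies in how the outcome is formed.

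The end of section III states the aim in terms of adverse-reaction incidence and the choice of agent. With no ranking in section IX (II) 3, a report could rest its conclusion on the adverse-reaction odds ratio.

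**Working it through.** **What can be reproduced.** The sample size of 600 is given without rates, effect size, power or allocation ratio, so it cannot be re-derived. The event rates cited for gadoterate in section IV (II) do reproduce: 241/2822 = 8.54% of patients with adverse events and 113/2822 = 4.00% possibly related. If both are patient counts, the attributed share is 113/241 = 0.469.

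**Inputs.**
- From the plan: two-sided 5% level; 600 patients; 8.5% as one event rate the documents give.
- Assumed: 300 per agent; the same true event risk r for both agents; attributed shares s1 (gadodiamide) and s2 (gadoterate). Event risks of 1%, 3% and 20% are added to show the range. The documents give no agent-specific shares for this trial.

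**Formulas.** Adverse-reaction risk p = r × s. Odds ratio = [p1/(1−p1)] / [p2/(1−p2)]. The false-positive rate is the chance that a pooled two-proportion test rejects, although event risk is equal.

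**Worked case, r = 8.5%, shares 60/40.**
- p1 = 0.085 × 0.60 = 0.0510, or 15.3 expected patients. p2 = 0.085 × 0.40 = 0.0340, or 10.2.
- Odds ratio = (0.0510/0.9490)/(0.0340/0.9660) = 1.53.
- Pooled standard error = √(2 × 0.0425 × 0.9575/300) = 0.0165. Unpooled = √[(0.0510 × 0.9490 + 0.0340 × 0.9660)/300] = 0.0165.
- Rejection rate = Φ[(0.017 − 1.96 × 0.0165)/0.0165] + Φ[(−0.017 − 1.96 × 0.0165)/0.0165], which is 17.8% with unrounded standard errors.

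**Range.** The rates at 1%, 3% and 8.5% are exact sums over all pairs of binomial counts. At 20% they are the normal approximation, which is within half a percentage point of the exact sum.

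| Event risk | 60/40: odds ratio | 60/40: false positives | 55/45: odds ratio | 55/45: false positives |
|---|---|---|---|---|
| 1% | 1.50 | 3.9% | 1.22 | 3.2% |
| 3% | 1.51 | 8.4% | 1.23 | 5.5% |
| 8.5% | 1.53 | 17.6% | 1.23 | 8.0% |
| 20% | 1.57 | 37.2% | 1.25 | 12.9% |

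The Wald test of the log odds ratio, which is what an unadjusted logistic model gives, is more conservative when events are few. Its exact rate for 60/40 is 3.2% at 3% events and 15.7% at 8.5%.

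**Anchored to the cited share.** With gadoterate at 0.469 and r = 8.5%, simulation gave an odds ratio of 1.29 and 9.9% rejection for a gadodiamide share of 0.60. For a share of 0.70 it gave 1.52 and 19.7%.

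**Check of the remedy.** With equal shares of 0.469 and r = 8.5%, the odds ratio is 1.00 and rejection is 4.9% (chi-square) or 4.1% (Wald). All-cause adverse events at equal 8.5% risk give 5.1% or 4.7%.

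**The case against.** Most of the remedy is arguably in the plan already. All adverse events are the primary outcome, the stated purpose compares them, and they are one of the two regression outcomes. Adverse reactions are not a listed primary or secondary outcome. This stands, and it limits the point to a missing ranking and to the serious-event definition. A reader might infer that the primary comparison is itself built on causality; the definition of an adverse event rules that out. Events are still collected with the agent apparently known, which is a separate and weaker matter.

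The causality section is also more structured than its opening words suggest. Most of its criteria do not depend on the agent, and a standard scale is used. That reduces the room for bias but leaves one agent-dependent criterion, applied by a rater who can see the agent.

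A reader might infer that the bias must favour the macrocyclic agent, since section III calls it safer. The documents do not support so firm a direction. Their case against gadodiamide concerns NSF and deposition, not ordinary reactions. For general reactions, section IV (II) gives 4.0% possibly related for gadoterate and presents 2.52% (10/397, in fact a share of reactions) as the gadodiamide incidence.

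A reader might also take open assessment as stated. It is inferred from the form and from the absence of any masking text. The trial-process figure is not available, and section IX (I) lists blind review without a procedure.

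Finally, the attribution shares are invented. That is so. They show what could happen, and at low event rates the effect is small.

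**Conclusion.** The point holds in limited form. Following the plan as written, differential attribution could produce a false agent difference in adverse reactions and in serious adverse events. Neither its size nor its direction can be determined from the documents. With 300 per agent and equal true event risk, both assumed, a 60/40 split gives an odds ratio of about 1.5 and false-positive rates of about 4%, 8%, 18% and 37% at event risks of 1%, 3%, 8.5% and 20%. A 55/45 split gives about 3%, 5.5%, 8% and 13%. The inflation therefore matters at the 8.5% event rate the protocol cites if attribution differs as much as 60/40, and is slight or absent at 1% to 3% under 55/45. The all-cause primary outcome does not depend on the causality call. This is a cheap improvement, not a flaw in the main comparison.

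**What to change.** In section IX (II) 3, state that the between-agent conclusion rests on the regression of all adverse events regardless of judged cause, in line with the primary outcome, and that the adverse-reaction regression is supportive. Report the comparison by the windows at the end of section III (up to 1 hour, 1 hour to 1 week, 1 week to 3 months) and separately for later follow-up; item 5 of the event form already records time to onset. For this comparison, count serious events regardless of cause. The same edit can name the scale levels that count as an adverse reaction.

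As an optional secondary safeguard, have an existing sub-investigator who did not give the injection complete item 16 with only generic name, manufacturer and batch hidden. Dosage and medication times should stay visible, because the causality criteria use them. Safety reporting stays unchanged. The masking is imperfect, since the item 12 narrative may name the agent. It also has to be decided before forms are rated, whereas section IX (II) 1 finalises the SAP only at last enrolment.

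The cost is a sentence or two in the SAP and, if wanted, one restricted form view. The downside is that all-cause events carry more background noise, especially in the 6 to 24 month follow-up, which is why the later period should be reported separately.

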This trial is a prospective, interventional study. According to the requirements of the study, 600 cases of patients with mild to moderate renal insufficiency were enrolled. Gadodiamide and gadoteric acid meglumine salt were used for enhanced MRI. Observe the adverse reactions within 60 minutes of using the gadolinium contrast agents; follow up by telephone at 3, 6, 12, and 24 months after the inspection.

III. Background information of clinical trials

The principle of Magnetic Resonance Imaging (MRI) relies on the magnetic field generated by water molecules in the human body. It has high resolution in soft tissues (such as the nervous system, parenchymal organs, and muscle tissue), and uses non-ionizing electromagnetic radiation. Known exposure risk, many imaging parameters (sequence, proton density, T1 and T2 relaxation time) and many other advantages, since it entered the clinic in the 1980s, it has been clinically proven to be a valuable imaging diagnostic method. In the early clinical practice, MRI was mainly used for unenhanced magnetic resonance imaging, and the value of Contrast Enhanced-Magnetic Resonance Imaging (CE-MRI) in the diagnosis of diseases was not recognized. In the later stage, due to CE-MRI in small lesions, inflammation, edema and tumor Such diagnostic advantages have become an important supplement to MRI. At least about 30% of disease MRI diagnosis requires injection of magnetic resonance contrast agents.

In 2000, Cowper described the mucoedema-like sclerosis skin disease of renal dialysis patients in the Lancet magazine, that is, Nephrogenic Systemic Fibrosis (NSF). In 2006, Grobner

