This experiment uses an electronic CRF form for manual review and computer inspection; follow the guidelines for filling in the CRF for this test; if there is questionable data after manual review or computer inspection, a data questioning form will be sent to the clinical trial unit and the investigator will sign and confirm the value Correction, data questioning and correction form should be kept.

(II) Statistical Analysis

1. Statistical Analysis Plan

The statistical analysis plan is led by the statistician, assisted by the data administrator, sponsor and researcher, and formulated through consultation. After the trial plan is finalized, statisticians are selected; when about 50% of the enrollment is completed, the statistical analysis plan is started, and the statistical analysis plan is determined when the enrollment of the last case is completed; the statistical analysis plan can be performed before the database is finally locked modify.

2. Sample size

This study is a post-marketing safety observation study, with a design sample size of 600 cases.

3. Statistical analysis sets and statistical methods

Because this trial is a safety monitoring study, the analysis set includes all patients who have used the study drug and have undergone safety evaluation.

The statistical analysis was done using SAS 9.4. This study does not estimate missing data.

All statistical tests are at the 5% level of significance, and the two-sided test may be expressed with a 95% confidence interval.

Describe the basic information of the patient, and use the mean, median, standard deviation, and range for continuous variables for statistical description. Categorical variables (nominal variables/ordinal variables) are described by frequency and frequency.

Calculate the number of adverse events, serious adverse events, adverse reactions and serious adverse reactions, the incidence and its 95% confidence interval, and the 95% confidence interval is calculated using the exact probability method. They are described separately according to the severity of adverse events and whether they are related to drugs.

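### For events after the 60-minute visit, the planned incidence and logistic regression ignore time at risk, so they are biased low to the extent that patients withdraw or are lost

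*Combined protocol and SAP*

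**What the plan says.** The primary outcome in the Protocol Summary is the incidence of adverse events. Section II (II) has patients observed for 60 minutes and then prescribes "follow up by telephone at 3, 6, 12, and 24 months after the inspection". The same schedule applies to every patient.

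Section IX (II) 3 fixes the analysis:

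- Estimate: "Calculate the number of adverse events, serious adverse events, adverse reactions and serious adverse reactions, the incidence and its 95% confidence interval".
- Interval: "the 95% confidence interval is calculated using the exact probability method".
- Denominator: "the analysis set includes all patients who have used the study drug and have undergone safety evaluation". No minimum length of follow-up is set.
- Missing data: "This study does not estimate missing data". No censoring rule is given.
- Comparison: logistic regression on whether an adverse event or reaction occurred, with agent among the covariates and no follow-up-time term stated.

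Section VI (II) 3 ends tracking and recording once a patient withdraws, apart from the reason. The Visit 2 to 6 form in section VI (III) collects "Time to onset of adverse events" (item 5) and, for deaths, "Time of death: y m d" (item 13). No stated analysis uses either. The form has no item for the date of last contact.

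**The concern.** A simple proportion with an exact interval suits a 60-minute window, in which nearly every patient is fully observed. It suits events collected over 24 months of telephone calls less well, because a patient who leaves at month 2 stays in the denominator and, having no recorded event, is counted as event-free at month 24. The logistic model treats that patient in the same way.

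Better records alone would not cure this. Even if every contact made is recorded perfectly, the stated methods do not use the length of observation. In a safety study the error runs in the unwelcome direction: late events are understated, and an agent whose patients are lost more often looks safer.

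**Working it through.** **Inputs from the documents.** 600 patients (section IX (II) 2); last contact at 24 months; two adverse-event figures from past trials of gadoterate meglumine in section IV (II), 241/2822 = 8.5% for any event and 113/2822 = 4.0% for possibly related events. These serve only as scenarios, since neither is a 24-month risk in this population.

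**Assumptions.** 300 patients per agent (no allocation ratio is stated); loss *d* by month 24 from 5% to 30%, with 40% as an extreme; loss independent of events; constant hazards.

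**The plan's own figure.** No incidence, precision, power or loss rate is stated, so there is nothing to reproduce. The 600 has no derivation.

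**Expected crude proportion.** With true 24-month risk *p*, *h* = -ln(1 - *p*) and *c* = -ln(1 - *d*):

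expected crude = *h*/(*h* + *c*) × [1 - (1 - *p*)(1 - *d*)]

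For *p* = 8.5% and *d* = 30%, *h* = 0.0888 and *c* = 0.3567, so the result is 0.1994 × (1 - 0.915 × 0.70) = 0.1994 × 0.3595 = 7.17%. The relative bias is 7.17/8.5 - 1 = -16%.

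**Coverage.** For each possible event count, form the 95% Clopper-Pearson interval and sum the binomial probabilities, at the expected crude proportion, of the counts whose interval contains the true *p*. Results for *p* = 8.5%:

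| Loss by 24 months | Expected crude | Relative bias | Coverage, n = 300 | Coverage, n = 600 pooled | Bias if all events fall in months 12-24 | Coverage, n = 300, same case |
|---|---|---|---|---|---|---|
| 0% | 8.50% | 0 | 96.2% | 96.0% | 0 | 96.2% |
| 5% | 8.29% | -2.5% | 96.4% | 95.7% | -3.8% | 96.3% |
| 10% | 8.07% | -5.0% | 96.2% | 94.7% | -7.6% | 95.7% |
| 20% | 7.63% | -10.2% | 94.7% | 89.9% | -15.3% | 91.7% |
| 30% | 7.17% | -15.7% | 91.4% | 80.7% | -23.3% | 82.8% |

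For *p* = 4.0% at n = 300 with a constant hazard, coverage is 95.3% at 20% loss and 93.7% at 30%. For *p* = 1% at n = 300 it stays at 98.9% or more at every loss rate tried, up to 40%.

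**Agent comparison.** With equal true risk of 8.5%, but 30% loss on one agent and 10% on the other, the apparent risk ratio is 7.17/8.07 = 0.89.

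**Does using time at risk repair it?** Kaplan-Meier was simulated at n = 300 with 3,000 runs. For a true 8.5%, the mean estimate was 8.50% at 20% loss (crude 7.63%) and 8.49% at 40% loss (crude 6.67%). Interval coverage across the scenarios run was 94.3% to 95.9%. With no loss, the Kaplan-Meier and crude estimates were identical (8.44% each).

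**The case against.** A reader might infer that the estimate and interval are simply wrong for late events. The documents do not support that. Every patient is scheduled for the same contacts, and if all are completed the crude proportion equals Kaplan-Meier and the exact interval is valid. A death before any event does not invalidate the crude proportion either. No loss rate is stated, so unequal observation is likely but not established.

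A reader might also infer that the agent comparison is already biased. The 0.89 ratio needs a 20-point difference in loss between agents, and nothing in the documents suggests one.

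The target is itself an inference. The plan does not define a 24-month incidence, and its text speaks of neither a crude proportion nor a binomial interval. The only windows named (section III) end at 3 months and are not carried into the analysis section. Over 3 months the problem nearly vanishes: constant loss reaching 30% at 24 months is 1 - 0.70^(3/24) = 4.4% at month 3, and a true 3-month risk of 8.5% would be reported as 8.3%. Still, the same form collects events to 24 months and no analysis window is set, so the incidence as written takes in the late events.

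Finally, a separate analysis plan is to be started at about half of enrolment and may be changed until lock. That makes a change feasible, but the protocol has already fixed the interval method and the logistic model; what it expressly leaves open is the model's variables.

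The core stands: early leavers remain in the denominator, tracking stops at withdrawal, and no rule covers incomplete follow-up.

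**Conclusion.** The point holds conditionally. Read as patients with an event over all evaluated patients, the planned incidence of events after 60 minutes is biased low to the extent that follow-up is incomplete, and the logistic comparison is biased if loss differs by agent.

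At 5% to 10% loss the bias is modest and coverage at n = 300 is essentially nominal. From about 20% loss the bias is material: about a tenth of the incidence under a constant hazard, and more if events come late. Interval coverage suffers mainly at 30% loss, in the pooled set of 600, or when events cluster in the second year. Rare events (about 1%) keep their coverage at 300 per agent, although the estimate carries the same relative bias. Acute events are unaffected.

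These sizes rest on assumed loss rates, independent loss, assumed event timing and 300 patients per agent. The plan should be changed because the better method costs little and gives the same estimate when follow-up is complete.

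**What to change.** Keep the exact binomial interval for the 60-minute incidence. For later events:

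- Report cumulative incidence of the first event by agent, with 95% confidence intervals, at 3, 6, 12 and 24 months. Use the Aalen-Johansen estimator, treat death that is not itself the event as competing, and censor at the last completed contact. Show the crude proportion alongside.
- Where event counts allow, compare agents with a complementary log-log or Cox model that uses time at risk. Otherwise report the cumulative-incidence difference with its interval. At 1% incidence, 300 × 0.01 gives about 3 events per agent, too few for a stable model.

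Costs: this is more than a change of SAP wording. A last-contact date must be added to the visit form and carried into the analysis file, including for patients without events. Late intervals will be somewhat wider. Onset times learned by telephone, with calls up to 12 months apart, depend on recall. Informative loss is not corrected by any of these methods, so loss by agent should be reported with the results.
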